3.6 Blinding and procedures for unblinding the study

3.6.1 Methods for ensuring blinding

The randomisation schedule, (emergency un-blinding tools), giving details of individual patient treatment will be produced by computer software that incorporates a standard procedure for generating random numbers. The material for the randomised period of treatment, will be supplied by Investigational Product Section at AstraZeneca, in containers as detailed in Section 3.4.3.

All study personnel will be unaware of the randomised treatment until all decisions on the evaluability of the data from all patients have been made and documented.

The study drug, fulvestrant, will be supplied by AstraZeneca, in the form of a single-dose in a pre-filled syringe. Each active pre-filled syringe will contain 250 mg of fulvestrant at a concentration of 50 mg/ml in a volume of 5 ml, designated a fulvestrant 5% weight/volume (w/v) injection. The placebo pre-filled syringe will look identical to the active pre-filled syringe and will also have a volume of 5 ml.

3.6.2 Methods for un-blinding the study

Individual treatment codes, indicating the treatment randomisation for each randomised patient, will be available to the investigator(s) or pharmacists at the study centre.

The treatment code must not be broken except in medical emergencies when the appropriate management of the patient necessitates knowledge of the treatment randomisation. The investigator(s) must document and report to AstraZeneca (or company representing AstraZeneca) any breaking of the treatment code. AstraZeneca retains the right to break the code for SAEs that are unexpected and are suspected to be causally related to an investigational product and that potentially require expedited reporting to regulatory authorities.

After the database lock for the primary analysis, in line with the IDMC advice, patients will have their treatment unblinded and transferred to open label supplies. Patients who are currently receiving fulvestrant 250 mg will be given the option to transfer to fulvestrant 500 mg.

After study treatment is unblinded, any patient not wishing to transfer to fulvestrant 500 mg, who remains on fulvestrant 250 mg, will receive only one 5 ml intramuscular injection, as the placebo injection previously required to preserve the double blind nature of the study is no longer needed.

3.7 Pre-study, concomitant and post-study treatment(s)

All prior treatments for cancer and all drugs given to, or taken by, the patient at entry and during the study must be clearly documented on the appropriate CRF page.

The following treatment restrictions apply:

- Concomitant anticancer treatments are not permitted during the study. Such treatments are prohibited even if they are given for another indication (e.g. megestrol acetate for appetite stimulation, or methotrexate for rheumatological disorders).
- Radiotherapy may be given concomitantly for control of bone pain if therapy was started prior to randomisation. Patients requiring radiation for breast cancer or surgery for a breast cancer site after randomisation will be considered to have progressed, unless the investigator specified otherwise. If the investigator rules out progression, then irradiated or excised lesions will be considered non assessable for response and will be monitored only for disease progression.
- Chronic concomitant bisphosphonate therapy for hypercalcemia, and bisphosphonate treatment for the prevention of bone metastases are not permitted during the study. Bisphosphonate therapy for the treatment of osteoporosis is permitted during the study. Bisphosphonate therapy at the time of randomisation for the management of bone metastases is recommended as standard of care. If bisphosphonate therapy is initiated after randomisation the reason for its use must be clearly documented.
- Sex hormone containing drugs such as hormone-replacement therapy (HRT), progestational agents (megestrol acetate), DHEA, other androgens (e.g., oxandrolone) and SERMs (e.g. raloxifene (Evista)) are not permitted during the study. In rare cases where patients suffer severe menopausal symptoms, management with non-hormonal agents, e.g., clonidine or venlafaxine, is recommended. Use of an oestrogen-containing vaginal ring is allowed.
- In addition, other drugs than those mentioned above which may affect sex hormone status or disease response, such as systemic ketoconazole, systemic corticosteroids and adrenocortical suppressants are not allowed to begin after randomisation in to the study. However, the patient can continue to receive such drugs if they were taken before randomisation and the investigator is satisfied that the patient's hormonal status is stable.
- Topical applications, inhaled sprays, eye drops, local injections and mouth-washes (if not swallowed), containing corticosteroids or ketoconazole are permitted during the study.

- Patients receiving long-term anti-coagulant therapy with warfarin are ineligible for the study unless they are receiving low dose warfarin and have an INR ≤ 1.6 . The INR should be checked to ensure that it is ≤ 1.6 prior to each injection. If the INR is > 1.6 , the injections should be withheld until the INR has returned to ≤ 1.6 . It is advised to apply direct pressure to the injection site in these patients.
- Patients who need to begin anti-coagulant therapy while receiving study treatment may be treated, at the discretion of the investigator, with low molecular weight heparin (LMWH). The LMWH should be temporarily discontinued 12-24 hours prior to each fulvestrant injection and then resumed 12-24 hours later (depending on the particular LMWH used). There is an increased risk of haemorrhage in these patients and the investigator should decide whether that risk is outweighed by the possible benefits of continued treatment. It is advised to apply direct pressure to the injection site in these patients.
- If, in the opinion of the investigator, warfarin is required instead of LMWH, it should be recognised that the risk of intramuscular haemorrhage may be increased. In this situation, the dose of warfarin should be chosen according to the condition being treated and the INR should be monitored. The INR should be checked prior to each injection and the injections may be withheld if the INR > 1.6 . It is advised to apply direct pressure to the injection site in these patients.
- Patients receiving antiplatelet therapy (ASA, ticlopidine, clopigrel, ...etc.) may be at increased risk of bleeding from intramuscular injection. The investigator should decide whether that risk is outweighed by the possible benefits of continued treatment. It is advised to apply direct pressure to the injection site in these patients.

Other medication, which is considered necessary for the patient's safety and well-being, may be given at the discretion of the investigator(s). The administration of all medication (including investigational products) must be recorded in the appropriate sections of the case report form (CRF).

Details of the first subsequent systemic breast cancer therapy received following discontinuation of randomised treatment (regimen and start and end date), as well as the best response to this therapy (according to the investigator's best judgment as per the RECIST criteria), will be collected.

3.8 Treatment compliance

The investigator or pharmacy must retain records of the administered pre-filled syringes. The CRA will check these records to confirm the compliance with the protocol administration schedule.

4. MEASUREMENTS OF STUDY VARIABLES AND DEFINITIONS OF OUTCOME VARIABLES

4.1 Primary variable

The primary variable for this study is time to progression (TTP), which is defined as the time from randomization to the time of the earliest objective disease progression, including death from any cause. Further detail is given in Section 4.6.1. TTP is used as the basis for the sample size calculation (see Section 6.5).

4.2 Screening and demographic measurements

Investigators should refer to the Study Plan (Table 1) for the list of procedures and assessments to be performed at screening and their relative timings prior to randomisation.

Before entering the study, patients will be assessed to ensure that they meet the eligibility criteria (see Sections 3.3.2 and 3.3.3). Patients not meeting these criteria should not be entered into the study.

Written informed consent must be obtained prior to any study specific assessments. Procedures that are part of standard of care may occur before informed consent is obtained.

Each patient will undergo screening procedures within 3 weeks prior to randomisation except for baseline tumour assessments (see below).

The data listed below will be collected on the relevant CRFs:

- date of birth and race
- past medical history, including all significant conditions which have existed previously even if now resolved
- physical examination to assess all conditions which are current and ongoing
- ECG
- WHO performance status
- haematology and biochemistry

Patients with any elevation of bilirubin, aspartate aminotransferase (AST), alanine aminotransferase (ALT) or alkaline phosphatase (ALP) above upper limit of reference range (ULRR) at screening must have a CT scan or ultrasound of the liver to assess involvement with hepatic metastases.

- concurrent therapy

- Tumour burden and tumour assessments (as per RECIST criteria (see Appendix C))
 - Tumour assessment data must be available for confirmation of disease before randomisation. All patients must have a chest x-ray or a computerized tomography (CT) scan of the chest within 4 weeks before treatment, and a screening skeletal survey or isotopic bone scan within 8 weeks before treatment. Patients with an abnormal isotopic bone scan or skeletal survey must have further baseline confirmation with assessment by X-ray (or by CT scan, or magnetic resonance imaging [MRI] as appropriate) for clinical evaluation and tumour assessment within 4 weeks prior to treatment. (A skeletal survey done within 4 weeks of treatment does not require further confirmation by X-ray.)
 - Up to 10 target lesions (no more than 5 lesions per organ) can be selected at screening; these target lesions, which must be measurable (as defined in Appendix C), will be monitored by the investigator throughout the study, and tumour measurements will be collected.
 - Previously irradiated lesions will not be considered measurable unless there is definite progression at such lesions immediately before entry, or if more than 12 weeks has elapsed between treatment and entry.
 - All other (non-target) lesions will also be monitored throughout the study, and an overall assessment of non-target lesions will be made and recorded as “present”, “present with progression” or “absent”.
- proven evidence of ER+ve breast cancer

If possible, the status of the PgR receptor should also be recorded. If the status of this receptor is not available historically, if possible a test should be done for the missing receptor data for the purposes of this study.

Screening data will be used as baseline measurements, except for haematology and biochemistry, which must be repeated before study treatment if study treatment does not commence within 7 days after the screening sample was taken. The most recent assessment before first dosing should be entered onto the Visit 1 CRF pages.

Day 0/Visit 1 is the day on which the patient first receives her randomised study treatment (ie, the first day to receive study treatment, not the day of randomisation).

The patient should be treated within 7 days following randomisation.

Subsequent visits should occur within ± 3 days of the protocolled visit times except for tumour assessments, which can occur ± 2 weeks of the specified time point.

4.3 Patient-Reported Outcomes (PROs)

The methods for collecting Patient Reported Outcomes (PRO) data are presented below.

QoL will be assessed for a sub-group of patients. This sub-group will initially include all patients in a number of selected countries. The QoL analysis will require a minimum of 100 patients and selection of participating countries will be based on availability of the translated questionnaires and suitability of investigators.

QoL will be assessed in both treatment groups using the Functional Assessment of Cancer Therapy – Breast (FACT-B) questionnaire (Appendix G).

The patient should complete a questionnaire at the scheduled clinic visit at baseline, and at each 4-weekly visit for 24 weeks or until progression, whichever occurs earlier. The patient should also complete a questionnaire at their treatment discontinuation visit if this occurs prior to 24 weeks. If any scheduled QoL assessment is not completed the reason for non-completion should be recorded.

Each centre participating with QoL assessments should allocate responsibility for QoL assessment to a specific individual (e.g., a research nurse). The AstraZeneca designee will provide training for the relevant personnel in the administration of QoL questionnaires to help avoid the key problem of missing data. Before patients are randomised, they must be informed of the rationale for the study and the study details, including the QoL questionnaire. The patients should be instructed on how to complete the questionnaire and if necessary assisted with completion of a training questionnaire that must be destroyed after completion.

It is important that the value and relevance of QoL data is explained carefully to participating patients so that they are motivated to comply with data collection. There is research evidence that patients with breast cancer value the opportunity to provide information on their QoL. The research nurse or appointed individual should also stress that the information is confidential. Therefore, if the patient has any medical problems she should discuss them with the doctor or research nurse separately from their QoL assessment.

The instructions for completion of questionnaires are:

- It must be completed before any investigations or discussions about the status of the patient's disease with the clinic staff.
- The patient must complete it herself without any intervention from family, friends, centre staff etc.
- The only exception to this is if the patient is blind or illiterate. In this case the questionnaire may be read to the patient verbatim, however the reader must not aid in the interpretation of questions or in the selection of answers.
- Only one answer to every question should be checked.

- Centre personnel should not review the responses to the questionnaire with the patient nor with any other centre staff.
- Following completion, the nurse or appointed individual may quickly scan the questionnaire for completeness and should confirm verbally with the patient that the questionnaire has been completed fully.

4.3.1 Methods of assessment

FACT-B consists of the FACT-G (general) QoL tool for cancer patients plus the Breast Cancer Subscale (BCS). FACT-G was developed by Pietras RJ ([Cella DF et al 1993](#)) using a standardized approach to derivation and reduction. It is a self-report instrument that measures multi-dimensional QoL. It consists of four domains: physical well-being, social well-being, emotional well-being, and functional well-being. The BCS was developed specifically for patients with breast cancer and is used in addition to FACT-G to measure overall QoL in these patients. FACT-B was chosen for use in this study because it has good psychometric properties, has been shown to be valid and responsive to change and known group differences ([Brady MJ et al 1997](#)), and is relatively simple and quick (up to 10 minutes) for patients to complete. FACT-B is in use in a number of large breast cancer treatment studies within the US and Europe.

4.3.2 Derivation or calculation of outcome variables

The main outcome measure from the FACT-B will be the Trial Outcome Index (TOI), which is a summary score of the following subscales:

- Physical well-being (PWB)
- Functional well-being (FWB)
- Breast cancer subscale (BCS)

The TOI is recommended as an efficient and precise summary measure of the physical and functional well-being of patients in clinical trials ([Brady MJ et al 1997](#)).

The following measures will also be derived from the FACT-B;

- The total FACT-B score comprising the sum of the scores from all the sub-scales; PWB, FWB, SWB, EWB, BCS.
- The total FACT-G score which comprises the sum of the scores from the PWB, FWB, SWB and EWB subscales

4.4 Health Economic measurements and variables (Not Applicable)

4.5 Pharmacokinetic measurement and variables (Not Applicable)

4.6 Efficacy and Pharmacodynamic measurement and variables

Following initial randomised trial treatment on day 0, subsequent visits and assessments, including day 14, should occur \pm 3 days of the protocolled visit times except for tumour assessments which can occur \pm 2 weeks of the specified visit date. Patients will be considered lost to follow-up if they miss their visit and have no information available for more than 24 weeks.

Efficacy for all patients will be assessed by objective tumour assessments every 12 weeks using the RECIST criteria (Appendix C) except for those patients with bone only disease.

All patients will be assessed until evidence of one of the following:

- Progression of disease
- Death without evidence of progression

For patients with measurable disease the RECIST criteria will be used to determine TTP, the objective tumour assessments (CR and PR), as well as the best overall objective tumour response; details are given in Appendix C. The revised (May 1999) WHO definitions (RECIST) for measurable, non-measurable, target and non-target, and the objective tumour response criteria (CR, PR, SD or progression of disease) are presented in Appendix C.

For patients with bone only disease, progression will be defined as described in Section 4.6.1.1.

Up to 10 target lesions (no more than 5 lesions per organ) can be selected at screening; these target lesions, which must be measurable (as defined in Appendix C), will be monitored by the Investigator throughout the study, and tumour measurements will be collected. All other (nontarget) lesions will also be monitored throughout the study, and an overall assessment of nontarget lesions will be made and recorded as “present”, “present with progression” or “absent”.

A patient is determined to have progressed if they have progression of target lesions, clear progression of existing non-target lesions, or the appearance of one or more new lesions (see Appendix C). Death will be regarded as a progression event in those patients who die before disease progression.

Lesions must be assessed using the same method and technique on each occasion. Lesions will be recorded on the CRF page in the same order as they were recorded at screening. Details of any new lesions will also be collected. Response and progression will be calculated in comparison to the baseline tumour measurements obtained before starting treatment.

Tumour markers must not be used to assign progression or objective response (see RECIST, Appendix C).

Objective tumour response will be determined using a computer program, and these responses will be used in the summaries of TTP, ORR, CBR, DoR and DoCB. Bone only disease patients will only be included in the TTP summaries.

Baseline radiological tumour assessments should be performed no more than 4 weeks before the start of study treatment. Further tumour assessments will be made for all patients at all time points defined in the study plan (Table 1).

It is important to follow the assessment schedule as closely as possible because TTP is the primary variable and biases in analysis can occur if 1 treatment group is examined more often or sooner than the other. If an unscheduled radiological and clinical tumour assessment is performed, and the patient has not progressed, the next scheduled tumour assessment should still be performed at the planned time (as detailed in the study plan). This is in order to minimize any unintentional bias caused by some patients being monitored at a different frequency than other patients.

Patients who are withdrawn from study treatment for reasons other than disease progression will continue to have objective tumour assessments every 12 weeks until progression is documented. After progression, patients should be followed up for survival every 12 weeks as outlined in the study plan, unless the patient withdraws consent. Adherence to the study plan should be observed whenever possible.

4.6.1 Time To Progression

4.6.1.1 Methods of assessment

For patients with measurable disease, the RECIST criteria will be used to determine a patient's TTP (see Appendix C).

According to RECIST, a patient is determined to have progressed if they have progression of target lesions, clear progression of existing non-target lesions, or the appearance of one or more new lesions. Progression of target lesions is defined as at least a 20% increase in the sum of the longest diameter (LD) of target lesions taking as references the smallest sum of LD recorded.

In the absence of measurable disease at baseline (as per RECIST criteria), the following will be considered progression among patients with lytic or mixed (lytic + sclerotic) bone lesions:

- The appearance of one or more new lytic lesions in bone
- The appearance of one or more new lesions outside of the bone
- Unequivocal progression of existing bone lesions

For patients with both measurable disease (as per RECIST criteria), and documented lytic or mixed bone lesions at baseline, the definition of progression will be based on the RECIST criteria in addition to the criteria defined above for patients with lytic or mixed bone lesions without measurable disease.

Note: Pathologic fracture, new compression fracture or complications of bone metastases will not be considered as evidence of disease progression, unless one of the above mentioned criteria is fulfilled.

The date of progression is the date of the investigation/procedure (imaging, biopsy, etc) that led to the diagnosis of progression. If more than one investigation/procedure is performed, and assuming that more than one confirms progression, the date of progression is the date when the first investigation/procedure was performed. The date of the progression in the case of a biopsy refers to the date of the biopsy itself and not the date of the pathology report. In the case of more than one procedure, where the first one had unclear results that have been confirmed later, that date of progression is the date of the investigation/procedure with clear, definitive results. Progression should not be backdated to the earlier procedure. If a patient dies prior to reporting progression, the date of progression should be considered as the date of death.

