3.3.2 Inclusion criteria

For inclusion in the study, patients must fulfil all of the following criteria:

1. Provision of written informed consent
2. Histological/cytological confirmation of breast cancer
3. Documented positive oestrogen receptor status (ER +ve) of primary or metastatic tumour tissue, according to the local laboratory parameters.
4. Requiring hormonal treatment:
 - (a) Relapsing during, or within 12 months of completion of, adjuvant endocrine therapy (tamoxifen, toremifene or aromatase inhibitors such as anastrozole, letrozole and exemestane), or
 - (b) Progressing on an endocrine therapy (tamoxifen, toremifene or aromatase inhibitors such as anastrozole, letrozole and exemestane) provided that this endocrine treatment was started at least 12 months after the completion of adjuvant endocrine treatment, or
 - (c) Progressing on an endocrine therapy (tamoxifen, toremifene or aromatase inhibitors such as anastrozole, letrozole and exemestane) given as first treatment for patients with *de novo* advanced* breast cancer

* Advanced breast cancer: Metastatic disease or locally advanced disease which is not amenable to treatment with curative intent.

5. Patients fulfilling one of the following criteria:
 - Patients with measurable disease as per RECIST criteria. This is defined as at least one lesion that can be accurately measured in at least one dimension (longest diameter to be recorded) as ≥ 20 mm with conventional techniques or as ≥ 10 mm with spiral CT scan.
 - Patients with bone lesions, lytic or mixed (lytic + sclerotic), in the absence of measurable disease as defined by RECIST criteria
6. Postmenopausal woman, defined as a woman fulfilling any 1 of the following criteria:
 - Age ≥ 60 years.
 - Age ≥ 45 years with amenorrhoea ≥ 12 months with an intact uterus.
 - Having undergone a bilateral oophorectomy.

- FSH and oestradiol levels in postmenopausal range (utilising ranges from the local laboratory facility).
 - In patients who have previously been treated with an LH-RH analogue, the last depot must have been administered more than 4 months prior to randomisation, menses must not have restarted, and FSH and oestradiol levels must also be in the postmenopausal range (utilising ranges from the local laboratory facility).
7. WHO performance status 0, 1 or 2.

For inclusion in the translational research component of the study, patients must fulfil the following criteria:

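### Sections 4.6 and 4.6.1.1 set conflicting progression rules for patients without measurable disease who also have non-measurable lesions outside bone

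*Protocol*

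**What the plan says.** **Entry.** Criterion 5 (Section 3.3.2) has two routes. One is measurable disease. The other is "Patients with bone lesions, lytic or mixed (lytic + sclerotic), in the absence of measurable disease as defined by RECIST criteria". The second route does not require disease to be confined to bone.

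**Section 4.6.** Efficacy is assessed in all patients "using the RECIST criteria (Appendix C) except for those patients with bone only disease". The exception is repeated for the progression definition: "For patients with bone only disease, progression will be defined as described in Section 4.6.1.1". The general rule in the same section, not limited to measurable disease, counts target-lesion progression, "clear progression of existing non-target lesions, or the appearance of one or more new lesions".

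**Section 4.6.1.1.** The special list opens with a different population: "In the absence of measurable disease at baseline (as per RECIST criteria), the following will be considered progression among patients with lytic or mixed" bone lesions. It has three items: "The appearance of one or more new lytic lesions in bone"; new lesions outside bone; and "Unequivocal progression of existing bone lesions". Patients with both measurable disease and such bone lesions get RECIST plus this list.

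**Section 4.6.1.2.** TTP takes its progression definition from Section 4.6.1.1.

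**Appendix C.** Section 3.2.2 counts unequivocal progression of any existing non-target lesion, and any new lesion, as progressive disease. Section 2.1 names ascites, effusions and lesions below the size threshold among non-measurable disease.

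**The concern.** The two sections describe the population of the special list in different terms: bone only in one, no measurable disease in the other. The second is wider. The patients in between have lytic or mixed bone lesions, no measurable disease, and non-measurable disease elsewhere. Section 4.6 leaves them under its general rule; Section 4.6.1.1 moves them to a list that ignores worsening of an existing lesion outside bone.

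At stake is whether, and when, such a patient has a primary-endpoint event. Section 4.6 says response feeding the TTP summaries is determined by a computer program, and a program needs one rule. Scheduled tumour assessment runs until progression, after which follow-up is for survival. If a site declares progression under Section 4.6 and the program follows Section 4.6.1.1, scans may stop with no derived event. The patient's TTP then either ends at death or is censored at her last disease assessment, close to the time she worsened. Such censoring would be potentially informative.

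**Working it through.** **Background figure.** The 632 events in Section 6.5 (HR 0.8, two-sided 5%, 80% power, 1:1) reproduce:

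- Schoenfeld: 4 × (1.960 + 0.842)² / (ln 0.8)² gives 631.
- Freedman: (1.8 / 0.2)² × (1.960 + 0.842)² gives 636.
- Power at 632 events: 80.1%.

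This point does not dispute or change that number.

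**Step 1: does the in-between group exist?** Criterion 5 does not bar non-measurable lesions outside bone. Exclusion criterion 1 removes brain or leptomeningeal involvement, extensive hepatic disease and symptomatic lymphangitic spread, but not effusions or small lesions as such. So a patient with lytic bone lesions plus an effusion can be enrolled, has no measurable disease, and is not bone only.

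**Step 2: the two sections side by side.**

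| Patient group | Finding | Section 4.6 | Section 4.6.1.1 |
|---|---|---|---|
| Measurable disease | Clear worsening of an existing non-target lesion outside bone | Progression | Progression (RECIST) |
| Measurable disease | New mixed or sclerotic bone lesion | Progression (new lesion) | Progression (RECIST, new lesion) |
| Bone only | Worsening outside bone | Cannot occur: no such lesion | Cannot occur |
| Bone only | New mixed or sclerotic bone lesion | Refers to 4.6.1.1 | Mixed unclear; sclerotic not listed |
| Bone lesions, no measurable disease, other non-measurable lesions | Clear worsening of an existing lesion outside bone | Progression | **Not listed** |
| Same group | New mixed or sclerotic bone lesion | Progression (new lesion) | Mixed unclear; sclerotic not listed |

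The direct conflict is the fifth row. The sixth adds a difference for new sclerotic lesions and an uncertainty for new mixed ones.

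**Step 3: is the list exhaustive?** It does not use the word only. Two features make it read that way. The note on fractures in Section 4.6.1.1 refuses progression unless one of the listed criteria is met, and Section 4.6.1.2 points to Section 4.6.1.1 for the definition of a TTP event.

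**Step 4: size.** The documents give neither the share of patients without measurable disease nor the share of their events that turns on the unlisted findings. Suppose, purely as an assumption, that 10–30% of the 632 events arise in patients without measurable disease and that 2–10% of those turn on an unlisted finding:

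- Low: 632 × 0.10 × 0.02 = 1.3 events.
- High: 632 × 0.30 × 0.10 = 19.0 events.

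This range of about 1 to 19 shows only how the answer moves with the inputs. It is not an estimate.

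**The case against.** The strongest defence is that the text can be read consistently. Section 4.6 exempts only bone-only disease from RECIST, so the patient with an effusion stays under RECIST, where non-target worsening counts; the list in Section 4.6.1.1 then adds bone criteria and removes nothing. That reading is possible, but the fracture note and the cross-reference in Section 4.6.1.2 weigh against it. Both sections also tie the use of RECIST for TTP to patients with measurable disease, which this patient does not have.

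Three further objections stand and limit the point.

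- A reader might infer that Section 4.6 contradicts Section 4.6.1.1 for every patient without measurable disease. It does not. Section 4.6 expressly hands bone-only patients to Section 4.6.1.1, and they have no existing lesion outside bone that could worsen.
- A reader might infer that a new mixed bone lesion is excluded outright. The protocol describes mixed as lytic plus sclerotic, so such a lesion can be read as containing a new lytic one. The wording is unclear, because the sentence introducing the list separates lytic from mixed, but exclusion is not established.
- A reader might infer bias in the treatment comparison, or that analysed events vary from site to site. The rule is the same in both blinded arms, and response for the TTP summaries is derived by program. Site readings can still affect when scanning stops, but no direction of bias is shown.

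**Conclusion.** The conflict is real for a limited group: patients without measurable disease who also have non-measurable lesions outside bone. For them, clear worsening of an existing non-bone lesion is a primary-endpoint event under Section 4.6 and Appendix C and is not on the Section 4.6.1.1 list. Followed literally, the definition that TTP cites misses that event. The silence on new mixed and sclerotic bone lesions is a secondary ambiguity.

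The number of affected events cannot be derived from the documents. It is probably small, because bone-only patients cannot take the non-bone route at all. A reader might infer a firm count of lost events, or a delay of a fixed number of scan intervals. Neither is supported: both shares in the range above are assumed, and another listed criterion, an additional scan or death could fix the event date sooner. The 632-event requirement is unaffected. The SAP is not among the documents reviewed, so it may already say which rule the program applied; the protocol's two sections would still disagree.

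**What to change.** 1. Use one population term in Sections 4.6 and 4.6.1.1, so that for patients who are not bone only the TTP derivation counts progression of existing non-target lesions outside bone, as Section 4.6 and Appendix C already state.
2. State explicitly how new mixed and new sclerotic bone lesions count. Adding only the word mixed to the list would still leave new sclerotic lesions out of line with Section 4.6 and Appendix C.
3. Derive TTP by that single rule from the recorded lesion data.
4. Sections 3.1 and 7.6 treat the primary analysis as already performed, and the synopsis gives a data cut-off of 28 February 2009. So document which rule that analysis used, and report the other as a sensitivity analysis where the data allow.

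The cost is wording, a small change to the derivation program and one additional run. One limit should be checked first. Section 4.6 describes a single overall assessment of non-target lesions, so the record may not separate worsening in bone from worsening elsewhere; the case report form is not shown. Confirmed progression also ends randomised treatment under the protocol. This fix concerns the derivation of TTP and the reconciliation of the two sections, and takes no position on when treatment should stop.
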